10.1 Expected Adverse Events (associated with LUM015)

No adverse events related to the administration of LUM015 were observed during the Phase 1 safety study. Prior to the Phase 1 study, LUM015 had not previously been used in humans. Our preclinical studies demonstrated that it was reasonably safe to proceed with a Phase 1 study in humans. Preclinical studies in rats showed no LUM015 related effects on clinical observations, FOB evaluation, body weights, food consumption, ocular condition, clinical chemistry, hematology and coagulation parameters or organ weight at doses up to 53-fold higher than in humans.

The results from the repeat dose toxicity study in dogs (performed by NCI) show that administration of 0.5 or 10.0 mg/kg of LUM015 intravenously once daily for seven consecutive days (8 total doses) did not cause any observable target organ toxicities. The only observable effect was hypersensitivity in several dogs. Notably, no hypersensitivity has been observed in the human patients that participated in the Phase 1 safety study.

Clinicians should be prepared for a possible hypersensitivity or allergic reaction to occur during each administration of LUM015. Standing orders should be in place in the event of a hypersensitivity or allergic reaction for immediate intervention including administration of diphenhydramine, prednisone or both. If a study subject develops a Grade 2 (or greater) hypersensitivity or allergic reaction as defined in CTCEA 4.03, Luminell should be contacted within 24 hours of the event:

To Luminell:
[name]
[contact]
Email: [contact]
[contact]

If this occurs, enrollment in the study should be held until after consultation with the FDA regarding the event is completed and a determination is made by the sponsor, principal investigator and FDA as to whether prophylactic treatment with diphenhydramine to subsequent subjects is warranted.

10.2 Monitoring of Laboratory Values

A CBC (red blood cells, white blood cells and platelets) and serum chemistry (alkaline phosphatase, total bilirubin, BUN, calcium chloride, glucose, LDH, phosphorous, potassium, total protein, SGOT [AST], SGPT [ALT], sodium) tests will be completed at the first post-operative visit during the routine follow up visit. We note that it is not standard of care to perform follow up blood tests unless abnormalities were identified prior to surgery. The investigator will review the laboratory reports for any abnormal post-operative laboratory valued and will determine if any results are clinically relevant.

LUMICELL COMPANY CONFIDENTIAL

This document is confidential. Do not disclose or use except as authorized.

Any abnormal values that are determined to be clinically significant will constitute adverse reactions and will be captured on the case report form. If a trend is noted of clinically significant laboratory findings (i.e. a specific event occurs in more than one patient), or if any serious adverse event that is possibly, probably or definitely related to LUM015 or the Imaging Device is reported, no additional patients will be recruited until an explanation can be found. The principal investigator will assess the likelihood that the adverse reaction or severe and/or serious adverse event resulted from LUM015. The FDA will be notified of any trends observed in clinically significant laboratory findings.

10.3 Expected Adverse Device Effects (associated with the LUM Imaging System)

To date, the LUM Imaging System has not been studied clinically. Thus, there are no known anticipated adverse device effects.

11. ADVERSE EVENT REPORTING REQUIREMENTS

11.1 Definitions

11.1.1 Adverse Event (AE)

An adverse event (AE) is any undesirable sign, symptom or medical condition or experience that develops or worsens in severity after starting the first dose of study treatment or any procedure specified in the protocol, even if the event is not considered to be related to the study. The severity of any possible AE observed will be classified per the grading established by the Common Terminology Criteria for Adverse Events (CTCAE) 4.03.

Abnormal laboratory values or diagnostic test results constitute adverse events only if they induce clinical signs or symptoms or require treatment or further diagnostic tests.

11.1.2 Serious adverse event (SAE)

A serious adverse event (SAE) is any adverse event, occurring at any dose and regardless of causality that:

- Results in death
- Is life-threatening. Life-threatening means that the person was at immediate risk of death from the reaction as it occurred, i.e., it does not include a reaction which hypothetically might have caused death had it occurred in a more severe form.
- Requires or prolongs inpatient hospitalization (i.e., the event required at least a 24-hour hospitalization or prolonged a hospitalization beyond the expected length of stay). Hospitalization admissions and/or surgical operations scheduled to occur during the study period, but planned prior to study entry are not considered SAEs if the illness or disease existed before

LUMICELL COMPANY CONFIDENTIAL

This document is confidential. Do not disclose or use except as authorized.

the person was enrolled in the trial, provided that it did not deteriorate in an unexpected manner during the trial (e.g., surgery performed earlier than planned).

- Results in persistent or significant disability/incapacity. Disability is defined as a substantial disruption of a person's ability to conduct normal life functions.
- Is a congenital anomaly or birth defect; or
- Is an important medical event when, based upon appropriate medical judgment, it may jeopardize the subject and require medical or surgical intervention to prevent one of the outcomes listed above. Examples of such medical events include allergic bronchospasm requiring intensive treatment in an emergency room or at home; blood dyscrasias or convulsions that do not result in inpatient hospitalization, or the development of drug dependency or drug abuse.

Events **not** considered to be serious adverse events are hospitalizations for:

- routine treatment or monitoring of the studied indication, not associated with any deterioration in condition, or for elective procedures
- elective or pre-planned treatment for a pre-existing condition that did not worsen
- respite care

11.1.3 Adverse device effect (ADE)

An adverse device effect (ADE) is an adverse event which is at least possibly related to the device. ADEs are not considered serious adverse events.

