In some surgeries when the tumor is near the skin, a thin layer of tissue may be left just under the skin. Preliminary data shows that high fluorescence from the skin may create artifacts when imaging the thin layer of tissue in the lumpectomy cavity. In order to analyze possible artifacts caused by skin's fluorescence, we will perform imaging of the external breast tissue (skin) with the LUM Imaging Device pre and post injection of the LUM015 dye. Our intent is for a physician or research assistant to obtain a baseline signal background measurement by placing the LUM Imaging Device on ipsilateral and contralateral breast skin. Images will be taken prior to injection to within 30 minutes post injection. This data may provide information for developing the patient-specific tumor detection algorithm. If the physician or research assistant deems that this procedure will add additional stress, the external breast imaging will not occur.

Pathology analysis:

[figure not shown]
The purple ink applied during the ex vivo imaging procedures with the LUM 2.6 Imaging Device will not interfere with standard pathology procedures (see Appendix B for a detailed pathology protocol). The purple ink will be applied to both surfaces of the shaved margin, except on the final shaved margin in which the purple ink will be applied only to the TB surface. All the resected specimens will be inked and processed per standard of care pathology procedures. After all the standard of care pathology procedures are completed, the study pathologist will review histopathology of areas marked with purple ink that designate areas of fluorescence identified by the LUM 2.6 Imaging Device and correlate fluorescence with histopathology findings. See Appendix B for details of the pathology procedures.

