5.8 Criteria for Stopping the Study

The events listed below are the stopping rules criteria for the study. In the case of any of these events, no additional patients will be recruited, dosed or imaged until an explanation can be found.

- Clinically significant laboratory findings that are deemed serious or severe (this includes if a trend is noted in clinically significant laboratory findings, see section 10.3)
- Any unanticipated adverse device effect (as defined in section 11.1.4)

LUMICELL COMPANY CONFIDENTIAL

This document is confidential. Do not disclose or use except as authorized.

- Hypersensitivity or allergic reactions of Grade 2 or greater as defined in CTCEA 4.03
- Any serious adverse event (as defined in section 11.1.2) that is considered either possibly, probably or definitely related to the treatment with LUM015 or the Imaging Device.
- Any other event that is deemed unacceptable in nature, severity, or frequency as assessed by the Investigator.

In the case that a safety event requiring enrollment suspension occurs, a prompt cumulative review of safety data and the circumstances of the event in question will be conducted to determine whether recruitment can be resumed, whether the protocol should be modified, or whether the study will be discontinued permanently. The FDA and reviewing IRB must be notified of any event that triggers suspension of enrollment in this study. If enrollment is suspended for safety reasons and it is deemed appropriate by the sponsor to resume the study, approval from the FDA and IRB must be obtained prior to resuming the study.

Regardless of whether recruitment is continued or not, all subjects injected with LUM015 or who were imaged with the LUM device at the time of study-stopping criteria were met will continue to be followed for safety.

In addition to the safety stopping rules outlined above, Lumicell may suspend or terminate this study at any time. The reasons for temporarily suspending or terminating the study may include but are not limited to the following:

- Subject enrollment is unsatisfactory.
- Non-compliance that might significantly jeopardize the validity or integrity of the study.
- Sponsor decision to terminate development.

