11.4 Reporting to Luminell

11.4.1 Serious Adverse Event Reporting

All serious adverse events that occur after the initial dose of LUM015 Imaging Agent must be reported to Luminell using the provided SAE form. This includes events meeting the criteria outlined in Section 11.1.2, as well as the following:

- Grade 2 (moderate) and Grade 3 (severe) Events – Only events that are unexpected and possibly, probably or definitely related/associated with the intervention including hypersensitivity and allergic reactions.
- All Grade 4 (life-threatening or disabling) Events – Unless expected AND specifically listed in the protocol as not requiring reporting.
- All Grade 5 (fatal) Events – When the subject is enrolled and actively participating in the trial OR when the event occurs within 30 days of the last study intervention.

Note: If the subject is in long term follow up, report the death at the time of continuing review.

The principal investigator must report each serious adverse event to Luminell within 24 hours of learning of the occurrence. In the event that the Investigator does not become aware of the serious adverse event immediately (e.g., subject sought treatment elsewhere), the principal investigator is to report the event within 24 hours after learning of it and document the time of his or her first awareness of the adverse event. Report serious adverse events by telephone, email or facsimile to:

To Luminell:
[name]
[contact]
Email: [contact]

LUMICELL COMPANY CONFIDENTIAL
This document is confidential. Do not disclose or use except as authorized.

[contact]

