11.4.3 Non-Serious Adverse Event and Adverse Device Effect Reporting

Non-serious adverse events and non-serious adverse device effects will be reported to Luminicell on the adverse events Case Report Forms.

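### Section 11.1.3 excludes device effects from the SAEs, against 11.1.2, 5.8, 10.2, 11.4.3 and 11.8; separately, 11.4.1 starts SAE reporting at the LUM015 dose, later than 11.1.1 and 11.8

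*Combined protocol and SAP*

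**What the plan says.** Section 11.1.2 sets the general rule: "A serious adverse event (SAE) is any adverse event, occurring at any dose and regardless of causality that" meets one of the listed outcomes. Section 11.1.3 then defines a subset of adverse events by attribution, "An adverse device effect (ADE) is an adverse event which is at least possibly related to the device", and closes by saying that "ADEs are not considered serious adverse events".

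Other sections treat device-related SAEs as possible. One criterion in 5.8 suspends recruitment, dosing and imaging for an SAE, as defined in 11.1.2, that is "considered either possibly, probably or definitely related to the treatment with LUM015 or the Imaging Device". Section 10.2 repeats that trigger for recruitment. Section 11.4.3 gives a reporting route for "Non-serious adverse events and non-serious adverse device effects", which implies that serious ones exist, and 11.8 speaks of device effects of both kinds.

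On timing, 11.4.1 requires reports to the sponsor for "All serious adverse events that occur after the initial dose of LUM015 Imaging Agent". Section 11.1.1 counts an event that "develops or worsens in severity after starting the first dose of study treatment or any procedure specified in the protocol", and 11.8 counts from the start of study intervention. Section 1.1, repeated in 5.2.2.2 for Phase B, plans "imaging of the external breast tissue (skin) with the LUM Imaging Device pre and post injection of the LUM015 dye".

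**The concern.** Seriousness and causality are separate attributes of an event, and 11.1.2 keeps them apart. The last sentence of 11.1.3 joins them again: once an investigator rates an event as possibly related to the device, it leaves the SAE class. Whoever follows 11.1.3 and whoever follows 11.1.2 would code the same event differently.

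That classification feeds three things: the SAE tabulation in 14.5, the 24-hour SAE report in 11.4.1, and the device part of the SAE stopping criterion. The question is live in Phase B because the imaging result there directs removal of further tissue, so a surgical complication could plausibly be rated as possibly device-related.

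The start point in 11.4.1 is a second, independent wording problem. It conflicts with the event window in 11.1.1 and 11.8, not with the stopping rule.

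**Working it through.** There is no figure to reproduce. The check sets the sections side by side and follows each kind of serious event through them.

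**Step 1: is the conflict real?** An ADE is by definition an adverse event, so an ADE that meets an 11.1.2 outcome is an SAE under 11.1.2. Under 11.1.3 it is not. Neither section yields to the other. The conflict is explicit.

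**Step 2: what does the UADE route catch?** Section 11.1.4 covers serious device effects not previously identified in the plan, and adds a catch-all for other unanticipated serious problems associated with a device. Section 10.3 states that no device effects are anticipated. Most serious device effects would therefore qualify. UADEs are a separate stopping criterion in 5.8, are treated as serious and reported on the SAE form within 24 hours under 11.4.2 with no dose condition, and are tabulated under 14.5.

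**Step 3: follow each kind of serious event.**

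| Serious event | Under 11.1.2 | Under 11.1.3 | Reporting to sponsor | Gap |
|---|---|---|---|---|
| Device effect classed as UADE, before or after dose | SAE | Not SAE | 24 hours, 11.4.2 | None in reporting or stopping |
| Possibly device-related, after dose, not classed as UADE | SAE | Not SAE | 11.4.1 if an SAE; otherwise only through its added grade-based criteria; 11.4.3 covers non-serious effects only | Classification, SAE table, SAE stopping criterion |
| Any cause, before dose, not classed as UADE | SAE | Depends on attribution | 11.4.1 does not apply | 24-hour sponsor report |

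An example for the second row is a serious complication after an image-guided shave that is rated as possibly device-related but judged a known surgical risk. The three headings of 11.4 cover SAEs, UADEs and non-serious events. If 11.1.3 is followed, this event has no named class.

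**Step 4: how wide is the second row?** After dosing, 11.4.1 also takes in unexpected related Grade 2 and 3 events, nearly all Grade 4 events, and Grade 5 events during participation or within 30 days of the last intervention. Many such events would reach the sponsor anyway. What 11.1.3 still disturbs is whether the event is called an SAE, appears in the SAE table, and is handled consistently under 5.8.

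**Step 5: who is affected by the start point?** In Phase B (10 to 50 subjects) the interval runs from pre-injection skin imaging to dosing, in those who have the imaging; it is omitted if judged to add stress. Section 4.1 counts a subject as enrolled only once the product has been given, so this device exposure also precedes formal enrolment. In Phase A, 5 of 15 subjects (5/15 = 33%) were imaged with no dose, so the 11.4.1 clock never started for them, although 1.1 promised them the same safety monitoring as dosed subjects. Phase A is complete, so that part is retrospective.

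**The case against.** The strongest reply is that the protocol works despite the sentence. Section 5.8 names its own definition, 11.1.2, which contains no device exclusion, so a careful reader applying the stopping rule never reaches 11.1.3. UADEs stop the study independently, and 5.8 also has a criterion for any event the investigator finds unacceptable. Before dosing, events still go on the case report forms (11.2) and to the IRB under its policy (11.5), and life-threatening complications go to the medical safety monitor at once (5.7). An independent reviewer follows the adverse event data, and Phase B safety is reviewed after every 10 subjects (12.2).

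All of this stands, and it rules out two stronger readings. A reader might infer that the device part of the stopping rule is empty. That would require 11.1.3 to override the definition that 5.8 expressly cites, and nothing says it does. A reader might also infer that serious device effects go unreported. The UADE route, together with the absence of any anticipated device effect in 10.3, speaks against that. Nor does a rating of only possible relation put an event outside the UADE class: 11.1.4 covers effects associated with the device and does not define that as stronger than possible.

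The reply does not remove the contradiction. It shows that other provisions usually catch the event. It leaves open the case not classed as a UADE, and it does not explain why 11.4.1 should start later than 11.1.1 and 11.8.

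**Conclusion.** The contradiction holds, with limited reach. If followed as written, 11.1.3 misclassifies a serious, possibly device-related event that is not a UADE. Such an event could be left out of the SAE table and treated inconsistently under the device part of the stopping criterion. In addition, 11.4.1 does not require a sponsor report of a serious pre-dose event that is not a UADE.

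A reader might go further and infer that pre-dose events would be missing from the safety analysis. The text does not support that: 11.4.1 governs reporting to the sponsor, while 14.3 bases the safety evaluation on all patients who enter the study.

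The conclusion assumes that investigators may apply 11.1.3 literally and that some serious events will be judged anticipated or surgical and so not UADEs. The documents give no rate for either. The expected count is probably small, but no figure can be derived.

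**What to change.** Reconcile 11.1.3 with 11.1.2, 5.8, 10.2, 11.4.3 and 11.8. Either delete its last sentence or limit it to non-serious device effects, so that a device-related event meeting 11.1.2 is an SAE.

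Separately, align the start point in 11.4.1 with 11.1.1 and 11.8. Those two are not worded identically (any protocol procedure in one, study intervention in the other), so one start point should be stated and used in all three; it should cover the pre-injection skin imaging.

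No change to the stopping criteria is proposed. The cost is two wording changes and, at most, an occasional additional SAE report.

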11.1.4 Unanticipated adverse device effects (UADEs)

Unanticipated adverse device effect (UADE) is any serious adverse effect on health or safety or any life-threatening problem or death cause by or associated with, a device, if that effect, problem, or death was not previously identified in nature, severity, or degree of incidence in the investigation plan or application, or any other unanticipated serious problem associated with a device that relates to the rights, safety or welfare of subjects.

11.1.5 Expectedness

Adverse events (AEs) and adverse device effects (ADEs) can be 'Expected' or 'Unexpected'.

11.1.5.1 Expected adverse event or adverse device effect

Expected AEs and ADEs are those that have been previously identified as resulting from administration of the agent or use of the device. For the

LUMICELL COMPANY CONFIDENTIAL

This document is confidential. Do not disclose or use except as authorized.

purposes of this study, an AE or ADE is considered expected when it appears in the current AE/ADE list, the Investigator's Brochure, the Instructions for Use or is included in the informed consent document as a potential risk.

Refer to Section 10.1 for a listing of expected adverse events associated with the study agent(s) and Section 10.4 for a listing of expected adverse device effects associated with the imaging device.

11.1.5.2 Unexpected adverse event or adverse device effect

For the purposes of this study, an AE or ADE is considered unexpected when it varies in nature, intensity or frequency from information provided in the current AE/ADE list, the Investigator's Brochure, the Instructions for Use, or when it is not included in the informed consent document as a potential risk.

11.1.6 Attribution

Attribution is the relationship between an adverse event or serious adverse event and the study treatment. Attribution will be assigned as follows:

- Definite – The AE or ADE is clearly related to the study treatment.
- Probable – The AE or ADE is likely related to the study treatment.
- Possible – The AE or ADE may be related to the study treatment.
- Unlikely - The AE or ADE is doubtfully related to the study treatment.
- Unrelated - The AE or ADE is clearly NOT related to the study treatment.

11.2 Procedures for Recording and Reporting Safety

The principal investigator will assess the occurrence of AEs, SAEs, ADEs and UADEs at all subject evaluation time points during the study.

All AEs, SAEs, ADEs and UADEs whether reported by the subject, discovered during questioning, directly observed, or detected by physical examination, laboratory test or other means, will be recorded in the subject's medical record and on the appropriate study-specific case report forms.

For events related to the imaging agent, the descriptions and grading scales found in the revised NCI Common Terminology Criteria for Adverse Events (CTCAE) version 4.0 will be utilized for AE reporting. All appropriate treatment areas should have access to a copy of the CTCAE version 4.0.

A copy of the CTCAE version 4.0 can be downloaded from the CTEP website at:

LUMICELL COMPANY CONFIDENTIAL
This document is confidential. Do not disclose or use except as authorized.

http://ctep.cancer.gov/protocolDevelopment/electronic_applications/ctc.htm

